Appendix

APPENDIX 1- RECIST 1.1

Subgroups that designated a response category (complete response [CR], partial response [PR], stable disease [SD] and progressive disease [PD], see definitions below) are all patients receiving at least one cycle of tamoxifen. All patients with an objective CR or PR response should have the response confirmed at least 4 weeks after the initial response documentation.

Radiological Response Rate

RECIST

The response and progression will be evaluated in this study using the new international criteria proposed by the RECIST (Response Criteria in Solid Tumors) committee.¹⁹ Changes only in the largest diameter (one-dimensional measurement) of tumor lesions are used in the RECIST criteria.

Measurable Disease. Measurable lesions are defined as those that can be accurately measured in at least one dimension (longer diameter to be recorded) as > 20 mm with conventional techniques (physical examination, CT, MRI) or as > 10 mm with spiral CT. All tumor measurements should be recorded in millimeters (or decimal fractions of centimeters).

The same evaluation method and the same technique should be used to characterize each lesion identified and reported in the baseline examination and during follow-up.

Clinical lesions: Clinical lesions will only be considered measurable when they are superficial (for example, cutaneous nodules, palpable lymph nodes). For the case of cutaneous lesions, the documentation is recommended by means of color photography, including a ruler to estimate the size of the lesion.

CT / MRI: Tomography and resonance are the best reproducible and currently available methods to measure target lesions selected for response assessment. Conventional CT and MRI should be performed with cuts of 10 mm or less in cross-section, contiguously. Spiral CT should be performed using a contiguous reconstruction algorithm of 5 mm. This applies to the chest and abdomen.

Unmeasurable disease. All other lesions (or disease sites), including small lesions (diameter greater than <20 mm with conventional techniques or <10 mm with spiral CT) are considered to be non-measurable diseases. Bone lesions, leptomeningeal disease, ascites, pleural / pericardial effusions, lymph nodes and cystic lesions are all non-measurable.

Target Injuries. All lesions measurable up to 5 lesions per organ and 10 lesions in the total representation of all involved organs should be identified as target lesions and be recorded and measured at the baseline examinations. Target lesions should be selected based on their size (lesions with the longest diameters) and their suitability for accurate repeated measurements (by techniques per image or clinically). The sum of the largest diameters (LD) of all target lesions will be calculated and reported on the baseline examinations. This will be used as a reference for the characterization of the objective tumor response. If there are > 10 measurable lesions, those not selected as target lesions will be considered, along with non-measurable diseases, as non-target lesions.

Non-target lesions. All non-measurable lesions (or disease sites) in addition to any measurable lesions and above 10 listed as target lesions. Measurements are not

required, but these lesions should be specified on the baseline examination and followed up as "absent" or "present".

All patients will have their BEST RESPONSE in the classified study as summarized below:

Complete Response (CR): disappearance of all clinical and radiological evidence of tumor (target or non-target), and subsequent confirmation at ≥ 4 weeks.

Partial Response (PR): a reduction of at least 30 percent in the sum of LD of target lesions, based on the baseline examination, and subsequent confirmation at ≥ 4 weeks.

Stable Disease (SD): state of equilibrium of the disease. Neither reduction sufficient to qualify as PR nor sufficient increase to qualify as PD, documented at least once > 4 weeks from the baseline examination.

Progression disease (PD): an increase of at least 20 percent in the LD sum of the lesions measured with reference to the smallest sum of LD registered since the beginning of the treatment. The appearance of new lesions will also constitute progressive disease. In exceptional circumstances, evident progression of non-target lesions may be accepted as evidence of disease progression.

TABELA 4 – Classificação de resposta conforme RECIST 1.1

Target lesions	Non Target lesions	New lesions	Overall response	The best answer to this category also requires
CR	CR	No	CR	Confirmation of > 4 weeks
CR	Non CR / Non PD	No	PR	Confirmation of > 4 weeks
PR	Non PD	No	PR	
SD	No PD	No	SD	Documented at least once > 4 weeks from baseline
PD	Any	Yes or No	PD	Not before SD, PR or CR

Any	PD*	Yes or No	PD	
Any	Any	Yes	PD	

* In exceptional circumstances, evident progression of non-target lesions may be accepted as evidence of disease progression.
 
Note:
 
Patients with significant clinical deterioration requiring discontinuation of treatment without objective evidence of disease progression should be described as "symptomatic deterioration - clinical progression". All efforts should be made to document objective progression even after discontinuation of treatment.

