- Histological diagnosis of well differentiated NET (typical and atypical lung carcinoids, NET G1, NET G2 of all gastroenteropancreatic sites and pancreatic NET G3 according to WHO 2017 classification) 20 advanced / metastatic, inoperable, with no possibility of curative treatment
- Immunohistochemical expression ≥ 1 percent for estrogen and / or progesterone receptor
- Disease with radiological progression (at least 10 percent tumor volume growth) in the last 12 months before day 1 cycle 1.
- No possibility of established treatments due to lack of access, risk of toxicities or without clinical indication. Patients who meet criteria for watchful waiting (low-dose disease and non-functioning NET) may be included.

- Measurable disease
- ECOG performance scale 0 to 2.
- Adequate organ function as defined by the following criteria:
 - serum aspartate aminotransferase (AST), serum alanine aminotransferase (ALT) \leq 2.5 times the upper limit of local laboratory normality (LSN-LL);
 - Total serum bilirubin \leq 2.0 x ULN-LL;
 - Absolute neutrophil count \geq 1,500 / mm³;
 - Platelet count \geq 80,000 / mm³;
 - Hemoglobin \geq 9.0 g / dL;
 - Estimated creatinine clearance by the MDRD equation \geq 30ml / min
 - Albumin \geq 3.5 g / dL;
 - INR \leq 1.5
 - Term of free and informed consent signed by the patient or legal representative.

Exclusion criteria

- Patients already on tamoxifen.
- Patients with aggressive disease requiring cytotoxic therapy or locoregional therapies (eg hepatic embolization)
- A history of serious clinical or psychiatric illness that, by clinical judgment, may involve participation risk in this study
- Patients participating in other protocols with experimental drugs.
- Patients with oral food difficulties.
- Patients who underwent major recent surgery less than 4 weeks previously.
- Patients receiving chemotherapy or other oncologic therapy for less than 3 weeks.

- Patients who use oral anticoagulation
- Previous history of deep vein thrombosis or pulmonary embolism in the last 12 months.
- Pregnant or lactating patients.
- Patients with postmenopausal vaginal bleeding with no defined etiology.
- Patients with breast cancer who need to use tamoxifen for this neoplasm
- Another synchronous neoplasm that requires systemic treatment

Treatment:

Tamoxifen:

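### Size-based progression has no millimetre minimum, so in a patient with one small target lesion a reading difference of about 2 mm can end disease control

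*Combined protocol and SAP*

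**What the plan says.** The primary outcome (Outcomes, Primary) is absence of radiological progression 24 weeks after starting tamoxifen, by RECIST 1.1 as set out in the appendix. Progression-free survival uses the same criteria.

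Appendix 1 gives three routes to progression: "an increase of at least 20 percent in the LD sum of the lesions measured with reference to the smallest sum of LD registered" since treatment began, a new lesion, or, exceptionally, evident progression of non-target lesions. The first route carries no absolute minimum. The appendix requires a confirmatory assessment for complete and partial response only.

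The appendix defines measurable lesions "as > 20 mm with conventional techniques (physical examination, CT, MRI) or as > 10 mm with spiral CT", and states: "Spiral CT should be performed using a contiguous reconstruction algorithm of 5 mm". The target set is "All lesions measurable up to 5 lesions per organ and 10 lesions in the total representation of all involved organs". The inclusion criteria ask for "Measurable disease" with no minimum number of lesions or minimum sum, and add: "Patients who meet criteria for watchful waiting (low-dose disease and non-functioning NET) may be included".

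Imaging is at baseline and every 12 weeks, so two scheduled scans fall by the primary time point. Under Study design and Treatment suspension criteria, radiological progression is also a reason to stop study treatment.

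**The concern.** A purely relative threshold shrinks with the tumour sum. Near the lower limit of measurability it comes down to about 2 mm, a size at which ordinary reading variation may matter. Two features add to this. The reference is the smallest sum so far, so one low reading at week 12 lowers the bar for week 24. And a single reading settles the matter, because progression needs no confirmation.

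The trial has one arm and is compared with a fixed 50% (Sample Size Calculation), so no control group shares the reading error. Each stable patient misread as progressing becomes a failure on the primary outcome and an event for progression-free survival. With 22 planned patients, one such patient moves the disease control rate by 1/22 = 4.5 percentage points.

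**Working it through.** **Inputs from the documents.** Threshold 20% over the smallest sum, no minimum in millimetres; spiral-CT lesions measurable above 10 mm; scans at baseline, week 12 and week 24 (all as cited above). The plan gives no figure for reading error or false progression, so there is none to reproduce.

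**Step 1: the rule in millimetres.** Required increase = 0.20 × smallest sum.

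| Smallest sum (mm) | Increase that counts as progression (mm) |
|---|---|
| 10 | 2.0 |
| 10.1 | 2.02 |
| 11 | 2.2 |
| 15 | 3.0 |
| 20 | 4.0 |
| 25 | 5.0 |
| 50 | 10.0 |

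A 2 mm increase suffices only when the smallest sum is 10 mm or less. From an 11 mm baseline, 2 mm is 2/11 = 18.2% and does not count. But readings of 11, 10 and 12 mm do count, since (12 − 10)/10 = 20%.

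**Step 2: how often a stable lesion would be called.** Assumptions: one target lesion of true diameter D, no growth, and independent normal reading errors with standard deviation SD. The documents give no SD; 1 to 2 mm is assumed, with 0.5 mm as a favourable case. Only baseline readings above 10 mm are kept, because others are not measurable. A patient is called at week 12 if that reading is at least 1.2 × baseline, or at week 24 if that reading is at least 1.2 × the smaller of the first two.

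Closed-form check for week 12 alone: the reading minus 1.2 × baseline has mean −0.2D and standard deviation SD × √(1 + 1.44) = 1.562 × SD. At D = 15 and SD = 1, z = 3/1.562 = 1.92, a probability of 2.7%. The second scan, judged against the lower of two readings, brings the total to 7%.

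Simulated false progression by week 24:

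| D (mm) | Rule as written, SD 1 / 1.5 / 2 mm | With a 5 mm minimum, SD 1 / 1.5 / 2 mm |
|---|---|---|
| 10.5 | 11 / 24 / 33% | 0.02 / 1 / 4% |
| 15 | 7 / 24 / 36% | 0.06 / 2.5 / 9% |
| 20 | 1 / 11 / 23% | 0.06 / 2.5 / 10% |

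At SD 0.5 mm the rule as written gives 0.4% at 10.5 mm and less at 15 and 20 mm. Rounding readings to whole millimetres changes the picture little: 14-31% at 10.5 mm for SD 1-2 mm, up to 14% with the minimum, and at most about 3% at SD 0.5 mm.

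**Step 3: where the minimum stops mattering.** 0.20 × 25 = 5, so from a smallest sum of about 25 mm the relative rule already demands 5 mm. For three stable lesions of 11-12 mm, false progression is about 1%, 5-6% and 12% at SD 1, 1.5 and 2 mm, with or without the minimum.

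**Step 4: the price of a minimum.** A 10.5 mm lesion would have to reach 15.5 mm, a rise of 5/10.5 = 48%. If it truly grows 2 mm per 12 weeks, then at SD 1 mm it is called by week 24 in 88% of cases under the present rule and in 11% with the minimum.

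**The case against.** The strongest reply is that the exposed group may be small. The population has advanced or metastatic inoperable disease, and all measurable lesions are summed, up to ten. Many patients may have sums above 25 mm, where the minimum does nothing. Allowing watchful-waiting patients does not show that any has a single 10 mm target. The appendix also keeps the imaging method constant and picks targets suited to repeat measurement, which should hold reading error down. All of this stands and limits the size of the point, but it does not remove the gap in the definition.

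A minimum also has its own bias: slow true growth may pass as control at week 24, which flatters the rate against a fixed 50%. That stands too, and is why both versions should be reported. Nor does any passage treat the 5 mm reconstruction interval as diameter error, so 5 mm is a choice tied to the protocol's imaging, not a derived error limit.

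A reader might infer several stronger things that the documents do not support:

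- **That 2 mm ends control for small lesions generally.** It does so only at a smallest sum of 10 mm or less.
- **That false progression reaches 21-51% at 10.5 mm.** That range comes from counting baseline readings of 10 mm or less, which are not measurable.
- **That a definite loss of disease control or power follows.** This would need a share of single-small-lesion patients and a decision rule, and the plan states neither.
- **That the appendix departs from the published criteria it names.** Their text is not in the documents.

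**Conclusion.** The point holds for patients with a small target sum. The plan's progression rule is purely relative, measured from the smallest sum and unconfirmed, and it decides the primary outcome. For a single stable target of 10.5 to 20 mm, the chance of a false call by week 24 ranges from about 1% to 36% at an assumed reading SD of 1-2 mm, and falls to about 0-10% with a 5 mm minimum. At SD 0.5 mm there is little to correct.

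These figures rest on independent normal reading errors, two scheduled scans and no true growth. The number of patients with a target sum below about 25 mm is not known, so no trial-level bias can be stated. Its direction is clear: false progression can only lower the observed disease control rate. The definition should be changed before analysis.

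**What to change.** For the analysis of the primary outcome and progression-free survival, define target-lesion progression in Appendix 1 as an increase of at least 20% over the smallest sum on study **and** an absolute increase of at least 5 mm. Keep the new-lesion and non-target routes and Table 4 as they are. Report the disease control rate under the purely relative rule as a sensitivity analysis, so that readers can see how many patients the minimum reclassifies.

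The cost is one clause and one extra tabulation. The downside should be stated in the plan: true growth of less than 5 mm in a single small lesion is called later and may count as control at week 24.

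Study design and Treatment suspension criteria also use radiological progression to end treatment. The sponsor should reconcile those passages with the endpoint definition, since a patient taken off treatment on a smaller increase might not be imaged long enough to be classified under the analysis rule. No stopping rule is proposed here.
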